## 11. STATISTICAL CONSIDERATIONS

### 11.1. Analysis Sets

**Enrolled Analysis Set (ENS)** – includes all enrolled patients.

Typically, summary tables of disposition and protocol deviations will be performed on the ENS.

**DLT Analysis Set** - includes all enrolled patients who receive at least 1 dose of Hu5F9-G4 or cetuximab and either experience a DLT or complete at least 4 infusions of Hu5F9-G4 and 2 infusions of cetuximab.

Patients who withdraw before completing the 4-week DLT assessment period for reasons other than a DLT, or who do not fulfill either of the criteria above, will not be evaluable for dose review decisions and will be replaced in the cohort.

**Efficacy Analysis Set (EAS)** - includes all enrolled patients who received at least 1 dose of Hu5F9-G4.

The analysis of ORR, DOR, DCR, PFS, OS, and TTP will be performed on the Efficacy Analysis Set.

**Safety Analysis Set (SAF)** – includes all enrolled patients who receive at least 1 dose of the study drugs.

Safety analysis and demographics, etc. will be performed using the SAF.

**Per Protocol Analysis Set (PPS)** – includes includes all enrolled patients who do not have any important or major protocol deviations that might affect the efficacy outcomes.

A sensitivity analysis of ORR may be performed on the Per Protocol Analysis Set.

**PK Analysis Set (PAS)** - includes all enrolled patients who receive at least 1 dose of study drugs and have measurable concentrations of Hu5F9-G4 from PK blood samples.

## **11.2. Sample Size Determination**

The total number of patients in this trial will include as many as 112 patients. This sample size includes the Phase 1b and Phase 2 parts of the study. In Phase 1b, a standard 3+3 dose escalation design will be used to explore the MTD of the investigational study drug combination in patients with solid tumors. An estimated 32 patients will be enrolled in Phase 1b, depending on dose escalation and expansion.

Phase 2 includes 2 arms, one comprising patients with KRAS mutant CRC and the other comprising patients with KRAS wild-type CRC, in which enrollment in one or both arms may be modified based on emerging data. A total of 88 patients (44 patients per arm) will be enrolled in Phase 2, assuming progression to Stage 2 for both arms. This sample size estimate was determined using a one-sided alpha level of 0.10 and a power of 0.80 based on a null hypothesis of 5% response rate compared to an alternative hypothesis of 15% for each cohort.

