## **Planned Number of Patients**

An estimated 15 to 24 patients will be enrolled in Phase 1b, depending on dose escalation and expansion.

Phase 2 includes 2 arms, one comprising patients with KRAS mutant CRC and the other comprising patients with KRAS wild-type CRC, in which enrollment in one or both arms may be modified based on emerging data. A total of 88 patients (44 patients per arm) will be enrolled in Phase 2, assuming progression to Stage 2 for both arms.

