**Sample Size Determination:**

The total number of patients in this trial will include as many as 112 patients. This sample size includes the Phase 1b and Phase 2 parts of the study. In Phase 1b, a standard 3+3 dose escalation design will be used to explore the MTD of the investigational study drug combination in patients with solid tumors. An estimated 32 patients will be enrolled in Phase 1b, depending on dose escalation and expansion.

Phase 2 includes 2 arms, one comprising patients with KRAS mutant CRC and the other comprising patients with KRAS wild-type CRC, in which enrollment in one or both arms may be modified based on emerging data. A total of 88 patients (44 patients per arm) will be enrolled in Phase 2, assuming progression to Stage 2 for both arms. This sample size estimate was determined using a one-sided alpha level of 0.10 and a power of 0.80 based on a null hypothesis of 5% response rate compared to an alternative hypothesis of 15% for each cohort.

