### **3. STUDY DESIGN**

#### **3.1. Overall Study Design**

This trial is an open label, multicenter Phase 1b/2 trial investigating the combination of Hu5F9-G4 and cetuximab in patients with solid tumor and patients with advanced CRC. The study will be conducted in 2 parts:

1. Dose escalation Phase 1b open to patients with solid tumors
2. Phase 2 study with 2 treatment arms in patients with advanced/metastatic CRC whose tumors are either KRAS mutant or KRAS wild-type

The Phase 1b dose escalation part of the study will be conducted using a standard 3+3 dose escalation design to determine the MTD, if one exists, and to identify a recommended Phase 2 dose (RP2D) of Hu5F9-G4 in combination with cetuximab. Up to 5 dose level cohorts are anticipated.

The Phase 2 part of the study will then incorporate a safety run-in by treating 9 patients with KRAS wild-type tumors at the RP2D. If the tolerability of the regimen is confirmed in CRC patients, the study will begin to accrue patients with advanced CRC who have KRAS mutant tumors and continue to accrue patients who have KRAS wild-type tumors and who are relapsed or refractory to an anti-EGFR antibody therapy. Additional safety run-in cohorts will not be required if other doses are tested in Phase 2. A total of up to 88 evaluable patients (44 patients with KRAS wild-type and 44 patients with KRAS mutant CRC) will be enrolled in the Phase 2 part. Patients who do not receive at least 2 doses of Hu5F9-G4 (of which at least 1 of the doses is a maintenance dose) may be replaced.

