1.3 Sample Size Determination

Depending on dose escalation and expansion, an estimated number of 15 to 24 patients will be enrolled in Phase 1b, and 88 patients will be enrolled in Phase 2.

No formal hypothesis testing will be done. In Phase 2, it is planned to enroll an expansion cohort of 44 patients with KRAS mutant CRC and another expansion cohort of 44 patients with KRAS wild-type CRC. This sample size was determined using a one-sided alpha level of 0.10 and a power of 80% based on a null hypothesis of 5% response rate compared with an alternative hypothesis of 15% for each cohort.

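### The stated maximum of 112 patients does not equal its own parts: 32 in Phase 1b plus 88 in Phase 2 is 120

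*Protocol*

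**What the plan says.** Four places give a Phase 1b number, and two of them also give a total.

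- Protocol Section 11.2 gives the total: "The total number of patients in this trial will include as many as 112 patients". It states that this takes in both phases. It then says "32 patients will be enrolled in Phase 1b, depending on dose escalation and expansion", and gives 88 for Phase 2 (44 per arm), conditional on both arms reaching the second stage.
- The synopsis paragraph on sample size determination repeats the 112, the 88 and the Phase 1b figure: "An estimated 32 patients will be enrolled in Phase 1b, depending on dose escalation and expansion".
- The synopsis paragraph on the planned number of patients has a different Phase 1b figure, again with 88 for Phase 2: "An estimated 15 to 24 patients will be enrolled in Phase 1b, depending on dose escalation and expansion".
- SAP Section 1.3 agrees with that second synopsis paragraph: "an estimated number of 15 to 24 patients will be enrolled in Phase 1b, and 88 patients will be enrolled in Phase 2". It states no overall total.

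On the make-up of Phase 2, Protocol Section 3.1 counts "up to 88 evaluable patients (44 patients with KRAS wild-type and 44 patients with KRAS mutant CRC", and SAP Section 1.3 says "it is planned to enroll an expansion cohort of 44 patients with KRAS mutant CRC and another expansion cohort of 44 patients" with KRAS wild-type disease. SAP Table 2 nevertheless lists three Phase 2 cohorts: one KRAS wild-type and two KRAS mutant, the latter on different Hu5F9-G4 regimens.

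**The concern.** A stated maximum should be at least as large as the sum of the estimates given beneath it. Here the estimates exceed it in the same paragraph, and the synopsis carries two Phase 1b figures that do not overlap (32 against 15 to 24).

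This matters for conduct more than for inference. Protocol Sections 3.9 and 6.3 say recruitment ceases when the stated number of patients is reached, and the protocol does not give one consistent number. The protocol is also the document that goes to the IRB/IEC, so the planned exposure of patients should be readable from it without a choice between versions.

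**Working it through.** **Inputs**

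- Maximum total: 112 (Protocol 11.2; synopsis, sample size determination).
- Phase 1b: 32 (the same two paragraphs).
- Phase 1b: 15 to 24 (synopsis, planned number of patients; SAP 1.3).
- Phase 2: 88, as 44 in each of two arms (all four places).
- Phase 2 sizing: one-sided alpha 0.10, power 80%, response rate 5% under the null and 15% under the alternative (Protocol 11.2; SAP 1.3).

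**Step 1. Reproduce the Phase 2 part.** 2 × 44 = 88, which agrees. The 44 also reproduces from its stated inputs with exact binomial probabilities.

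- Single stage, activity declared at 5 or more responses in 44: alpha = P(X ≥ 5 | n = 44, p = 0.05) = 0.0675, and power = P(X ≥ 5 | n = 44, p = 0.15) = 0.810. This is the smallest single-stage size that meets both targets.
- Two stages, 29 then 44, stopping at 1 or fewer responses in the first 29 and declaring activity at 5 or more in 44: alpha 0.0655, power 0.801. No two-stage design with a smaller maximum meets both targets.

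The response thresholds are derived here; the documents state none. The check leaves out the 15-patient interim analysis in Protocol Section 11.4. Its purpose is only to show that 88 is not the part at fault.

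**Step 2. Add the parts given with the total.** 32 + 88 = 120. Excess over the stated maximum: 120 − 112 = 8 patients, and 8 / 112 = 7.1%.

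**Step 3. Try the other Phase 1b figure.** 15 + 88 = 103 and 24 + 88 = 112. The stated total matches the upper end of that range exactly.

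**Step 4. See whether the escalation rules settle the Phase 1b figure.** Protocol Sections 3.1 and 3.2.2 allow up to 5 cohorts of 3 to 6 patients. That is 5 × 3 = 15 to 5 × 6 = 30 if all five cohorts are opened, before replacements and before expansion by up to 6 at a dose level already found safe. Neither 24 nor 32 follows uniquely from these rules, so they do not show which figure was meant.

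**Result**

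| Phase 1b figure | Phase 2 | Sum | Against 112 |
|---|---|---|---|
| 32 | 88 | 120 | 8 above |
| 24 | 88 | 112 | equal |
| 15 | 88 | 103 | 9 below |

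**The case against.** The best defence is that nothing turns on the figure. The Phase 1b number is an estimate; actual enrollment follows the 3+3 rules and steering committee decisions. Protocol Section 3.9 lets the recruitment number rise for replacements and for intermediate-dose or expanded cohorts. SAP Section 1.3 is consistent with 112 at its upper end.

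Most of that stands, and it limits the severity. It does not remove the error. The total is worded as a ceiling, and the estimate beneath it already exceeds that ceiling. Replacements and added cohorts can only raise the total, so they cannot explain a sum that is too high. The SAP's precedence clause concerns analysis methods; it does not clearly settle an enrollment figure, and it does not correct the protocol.

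A reader might be tempted by three stronger readings, none of which the documents support.

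- *That the Phase 2 sample size or its power is wrong.* The 44 per arm reproduces from its stated inputs. The documents do not say whether the 80% comes from a single-stage or a two-stage calculation. Section 11.2 refers to a second stage and 44 fits both, so the sponsor should not be told to label it single-stage.
- *That 112 is a hard limit which enrollment would breach.* Section 3.9 allows the number to be increased.
- *That the second KRAS mutant cohort in SAP Table 2 makes the 88 wrong as well.* Protocol Sections 3.1 and 11.2 and SAP Section 1.3 count the 44 by KRAS status, which suggests that both dose cohorts share it. Note b to the study design schema and Protocol Section 3.3 do allow further patients for an alternative regimen, so the place of this cohort is left unstated. That is a missing detail, not an arithmetic error.

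**Conclusion.** The point holds. The 112 in Protocol Section 11.2 and in the synopsis paragraph on sample size is inconsistent with the 32 and 88 beside it, by 8 patients or 7.1%. It agrees only with a Phase 1b upper limit of 24, which appears in two other places.

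The conclusion rests on addition of printed figures and needs no outside assumption. Which figure is out of date is not known. One possibility is that the Phase 1b estimate was updated without the total, but the documents do not say so.

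This is a minor-to-moderate consistency error. The size of each Phase 2 arm, the stated alpha and power and the response rates behind them are unaffected. The analyses are descriptive, and the SAP states "No formal hypothesis testing will be done", so no analysis is invalidated.

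**What to change.** Choose one Phase 1b figure and use it in all four places: Protocol Section 11.2, the two synopsis paragraphs and SAP Section 1.3. Restate the total as that figure plus Phase 2: 120 if 32 stands, 112 if an upper limit of 24 stands.

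Optionally, add one sentence to SAP Section 1.3 saying whether KRASm Cohort 2 is inside the 44 KRAS mutant patients or additional to them. If it is additional, count it in the Phase 2 number and in the total.

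The cost is a few restated figures in the SAP and a wording amendment to the protocol, which goes to the IRB/IEC under Protocol Section 12.3. The correction itself adds no patients and no procedures.

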## **11.3. Statistical Methods**

All analyses will be descriptive in nature. Descriptive statistics will be provided for all safety and efficacy endpoints.

All analyses will be conducted separately for patients in Phase 1b and Phase 2 parts of the study. However, safety analyses may be conducted for patients in both Phase 1b and Phase 2. In addition, efficacy analyses will be conducted separately for the two cohorts in Phase 2.

For continuous variables, the mean, standard deviation, median, and ranges will be provided. For categorical variables, the frequency and percentage in each category will be provided along with confidence intervals for primary and secondary efficacy endpoints. For time-to-event variables, the Kaplan-Meier (KM) estimates and corresponding two-sided 95% confidence intervals for the median and quartiles will be provided. The KM plot may also be provided. Details regarding the statistical

analysis to be conducted, including the handling of missing data and patient withdrawal, will be provided in the SAP.

### **11.3.1. Efficacy Analyses**

Endpoints used in the efficacy analysis are ORR, DOR, DCR, PFS, OS, and TTP.

#### **11.3.1.1. Objective Response Rate**

Objective response is defined as CR+PR determined by RECIST v 1.1 (primary efficacy) and iCR+iPR determined by iRECIST (secondary efficacy) separately. ORR is defined as the proportion of patients with objective response in the Efficacy Analysis Set.

A sensitivity analysis of ORR will be conducted on the Per Protocol Analysis Set if more than 10% of patients in the Efficacy Analysis Set are excluded from the Per Protocol Analysis Set.

#### **11.3.1.2. Disease Control Rate**

Disease control is defined as CR+PR+SD determined by RECIST v 1.1. DCR is defined as the proportion of patients with disease control in the Efficacy Analysis Set.

#### **11.3.1.3. Duration of Response**

DOR is measured from when the first (objective) response is met (i.e., CR or PR) until the first date of objectively documented progressive disease. Patients who do not have objectively progressive disease will be censored at their last documented progression-free date.

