## **6.2. Post-therapy Follow-up and Patient Study Completion**

Patients who complete, terminate, or decline further treatment should be encouraged to return for an End of Treatment Visit for evaluation of safety within 1 week of the decision to end Hu5F9-G4 treatment. The studies to be performed at end of treatment are listed in the Schedules of Assessments (SOAs), [Section 7.4](#). It is strongly encouraged that patients return for their Safety Follow-up Visit 30 days ( $\pm$  1 week) after the last dose of last study drug received. The Safety Follow-up Visit assessments are described in [Section 7.5](#).

Patients are considered to have completed study drug treatment when they finish the Safety Follow-up Visit 30 days ( $\pm$  1 week) after their last dose of the last study drug received, unless they are experiencing ongoing drug-related AEs and serious adverse events (SAEs). For patients being followed for ongoing AEs or SAEs, follow-up visits will continue at least every 4 weeks until resolution to baseline or stabilization of these events, unless the patient starts another anti-cancer therapy. Follow-up for ongoing AEs or SAEs after the Safety Follow-up Visit will stop if a patient begins another anti-cancer therapy.

All patients, including those who discontinue study treatment early, will be followed for response until progression and for survival for 5 years from the date of enrollment. For any patient who dies during this period, the cause of death must be reported to the Sponsor. Patients are considered to have completed study participation when they are no longer followed for disease progression or survival.

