#### **10.3.1.3. Response and Stable Disease Duration (RECIST 1.1 and iRECIST)**

Response duration will be measured from the time measurement criteria for CR/PR or iCR/iPR (whichever is first recorded) are first met until the first date that recurrent or progressive disease is objectively documented, taking as reference the smallest measurements recorded on study (including baseline).

Stable disease duration will be measured from the time of start of treatment until the criteria for progression are met, taking as reference the smallest sum on study (including baseline).

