#### **11.3.1.4. Progression-free Survival**

PFS is measured from dose initiation until the first date of objectively documented progression disease or death. Patients who do not have objectively documented progression disease AND not died will be censored at their last documented progression-free date.

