#### **11.3.1.6. Time to Progression**

TTP is measured from dose initiation until the first date of objectively documented progressive disease. Patients who do not have objectively documented progressive disease will be censored at their last documented progression-free date.

**Note:** Term “objectively documented progressive disease” above refers to PD in the overall response evaluation form.

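### The only duration-of-response rule in force censors a responder who dies without documented progression, although PFS counts that death; the SAP lists DOR but neither defines it nor records dropping it

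*Protocol*

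**What the plan says.** - **DOR, protocol Section 11.3.1.3 and synopsis.** DOR runs from first response "until the first date of objectively documented progressive disease". The censoring sentence is: "Patients who do not have objectively progressive disease will be censored at their last documented progression-free date".
- **What counts as progression.** The Note closing protocol Section 11.3.1.6 says the term "refers to PD in the overall response evaluation form".
- **Response duration, protocol Section 10.3.1.3.** It runs "until the first date that recurrent or progressive disease is objectively documented". Death is not mentioned, and there is no censoring rule.
- **PFS, protocol Section 11.3.1.4.** "PFS is measured from dose initiation until the first date of objectively documented progression disease or death". SAP Section 4 also counts death.
- **TTP, protocol Section 11.3.1.6.** "TTP is measured from dose initiation until the first date of objectively documented progressive disease". SAP Section 7 drops this endpoint.
- **Method, protocol Section 11.3.** "For time-to-event variables, the Kaplan-Meier (KM) estimates and corresponding two-sided 95% confidence intervals for the median and quartiles will be provided".
- **SAP.** Section 1.2 lists DOR among the secondary endpoints. Section 4 covers best response, ORR, PFS and OS only. Section 7 records that TTP and the iRECIST assessment are not reported and is silent on DOR. Section 1 gives the SAP's methods precedence where they differ from the protocol's.
- **Follow-up.** Under protocol Section 6.2 all patients "will be followed for response until progression and for survival for 5 years from the date of enrollment". Section 7.6 follows patients to progression or to the start of new anti-cancer therapy. Section 7.7 asks about progression every 3 months, by visit or telephone.

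**The concern.** A responder who dies without progression on the response form has stopped responding in any practical sense. The DOR rule treats that patient as if the response went on unobserved, with the same outlook as responders still at risk. Kaplan-Meier censoring assumes this, and death in advanced cancer gives reason to doubt it. The same death ends PFS. With TTP dropped, DOR is the only remaining time-to-event endpoint in which death is not an event, and neither document gives a reason or a competing-risk method.

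The SAP would be the place to settle this, but it has no DOR text that could take precedence. If DOR is reported, the protocol rule and Kaplan-Meier apply by default, to a handful of responders, and the reader has nothing to explain why one death is handled in two ways.

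**Working it through.** **1. One patient, two rules.** Take a responder who dies with no PD on the response form.

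| Endpoint | Event | This patient |
|---|---|---|
| PFS (protocol 11.3.1.4, SAP 4) | progression or death | event at death |
| DOR (protocol 11.3.1.3, synopsis) | PD on the response form | censored at the last date known to be progression-free |

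The SAP has no DOR method to set against the second row, so that row stands.

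**2. Can such patients arise?** Section 6.2 and the 3-monthly contacts make them fewer. They do not rule them out: Section 7.6 allows scans to stop at new therapy while survival follow-up continues, and nothing says whether progression learned by telephone becomes PD on the response form.

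**3. Number of responders.** The documents give no DOR figure to reproduce. Their Phase 2 size of 44 per arm does reproduce: in an exact binomial test of 5% against 15%, success at 5 or more responses in 44 gives one-sided alpha 0.0675 and power 0.8097. Expected responders are 0.15 × 44 = 6.6, about 7, or 0.05 × 44 = 2.2 at the null rate. SAP Table 2 has two KRAS-mutant dose cohorts. With an assumed 22 patients in one of them, 0.15 × 22 = 3.3, about 3.

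**4. Effect when death is close to the last scan.** Let q be the share of responses ended by death without documented PD. The documents do not give q; 5% to 20% is assumed. With total constant hazard λ, the progression-only hazard is (1 − q)λ, so the median ratio (deaths censored ÷ deaths counted) is 1/(1 − q). The chance of at least one such death among n responders is 1 − (1 − q)^n. The last two columns come from simulation (20,000 runs per cell, assumed median 6 months, deaths censored at the last 8-weekly scan, no other censoring).

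| q | Median ratio | At least one such death, n = 7 | n = 3 | Kaplan-Meier median longer with deaths censored, n = 7 | n = 3 |
|---|---|---|---|---|---|
| 5% | 1.05 | 30% | 14% | 11% | 4% |
| 10% | 1.11 | 52% | 27% | 21% | 8% |
| 20% | 1.25 | 79% | 49% | 40% | 17% |

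In most simulated trials the observed median is not lengthened.

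Invented example: 7 responders with times 2, 3, 4, 5, 6, 8 and 10 months, those at 3 and 5 being deaths without PD.
- Deaths censored: survival is 6/7 = 0.857 at 2 months, × 4/5 = 0.686 at 4, × 2/3 = 0.457 at 6. Median 6.
- Deaths counted: survival is 4/7 = 0.571 at 4 and 3/7 = 0.429 at 5. Median 5.

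**5. Effect when death comes long after the last scan.** Invented example: 7 responders, PD at 2, 4, 6, 8, 10 and 12 months; the seventh has a last scan at 1 month and dies at 20.
- Protocol rule: 6 at risk from month 1; survival is 3/6 at 6 months. Median 6.
- Progression or death with no gap rule: 7 at risk; survival is 4/7 at 6 and 3/7 at 8. Median 8.

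With 3 responders (PD at 5 and 8; last scan at 4, death at 20) the medians are 5 and 8. Here counting the late death lengthens DOR.

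Adding an assumed exponential gap with mean 12 months before death to the step 4 simulation (n = 7; q = 5%, 10%, 20%), simply counting every death lengthens the median in about 6%, 12% and 20% of trials and shortens it in about 3%, 6% and 12%. With a 6-month mean gap and q = 20%, it lengthens in about 14% and shortens in about 20%.

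**The case against.** **A progression-only DOR is a choice, not a contradiction.** The synopsis and Sections 10.3.1.3 and 11.3.1.3 agree with one another, TTP is also defined without death, and no passage requires DOR and PFS to treat a death alike. This stands: a reader might infer that the protocol contradicts itself, and it does not. What remains is a rule that censors a possibly informative event, without a stated reason, for an endpoint the SAP leaves undefined.

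**The rule does not always lengthen DOR.** This also stands. A reader might infer from the ratios in step 4 that DOR is overstated by 5% to 25%. Those ratios rest on constant hazards, an assumed q and death close to the last scan. Step 5 shows the direction can reverse when scanning stops early and death is late. A bare progression-or-death definition would therefore bring its own distortion, and the remedy has to deal with gaps and new therapy.

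**DOR may never be reported.** SAP Section 4 plans no DOR analysis, so the harm is conditional. But Section 7 records what was dropped, and DOR is not there; silence is not a recorded decision. DCR has a similar gap: it is listed in SAP Section 1.2, is not named in Section 4, and is not recorded as dropped.

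**Follow-up will usually document progression first.** Probably so, and this limits the number of cases. Step 2 shows why it need not remove them.

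**Conclusion.** The point holds in a limited form. On the text, a responder who dies without documented PD is censored for DOR and counted for PFS, and the SAP neither defines DOR nor drops it. That part rests on no assumption.

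The size is uncertain. If death comes soon after the last scan, censoring it tends to lengthen DOR, by a median ratio of 1.05 to 1.25 for an assumed q of 5% to 20%. If death comes long after assessments stopped, the direction is open. The documents do not show that DOR will be overstated, or that it will be reported at all. With about 7 responders per arm, or about 3 in a split cohort, the median is imprecise under any rule.

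DOR is secondary and descriptive. ORR, the 44 patients per arm and the interim rule are unaffected. The change is worth making before analysis, because it costs little and a later choice could look driven by the data.

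**What to change.** In SAP Section 4, add a DOR definition along these lines:

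- **Population:** patients with a confirmed CR or PR per RECIST v1.1.
- **Start and end:** from the date response criteria are first met to the first documented RECIST v1.1 progression or death from any cause, whichever is earlier.
- **Alive without progression:** censor at the last tumor assessment.
- **New anti-cancer therapy before progression or death:** censor at the last adequate tumor assessment.
- **Death after a long gap without assessments** (for example two or more missed scheduled scans): censor at the last adequate tumor assessment.
- **Method:** Kaplan-Meier by cohort.

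List the change in SAP Section 7, and align the protocol synopsis and Section 11.3.1.3. Editing Section 10.3.1.3 is optional, since it is not the analysis definition. If DOR will not be analyzed, record that in Section 7 instead, as was done for TTP. The status of DCR can be settled in the same entry.

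Cost: one SAP definition, one Section 7 entry and two short protocol edits. Death dates and subsequent therapy are already collected, so no new data are needed. Reported DOR may shift slightly, usually shorter. Censoring at new therapy or after a gap may itself be informative, so the number of responders censored for each reason should be shown beside the estimate.
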